## 1. Abstract

Major surgical procedures for cancer treatment are complex and are very difficult to recover from. The majority of patients have a complication, and may have long-term cognitive or physical problems. Finding ways to improve mobility and walking may help improve how patients recover from surgery. Only 1 in 4 hospitalized patients walk outside their room during hospitalization, and patients spend 95% of their hospitalized time in bed. However, there are few studies to show if this can be successful, and how to best motivate patients to walk. We want to evaluate how patients do after a radical cystectomy (removal of the bladder), to see if those receiving social support walk more and have less complications than those who receive the usual care. Our central hypothesis is that social incentives and support will increase how patients walk after complex surgeries, and will decrease healthcare utilization such as readmissions. This project will be a randomized trial comparing standard practice compared to social incentives and gamification postoperatively. The primary outcome is the number of steps per day, with secondary outcomes of postoperative readmissions. This will be the first trial of its kind to test if a simple strategy to increase walking in patients with bladder cancer can improve how patients do after surgery, and may be scalable for other major surgeries.

## 2. Overall objectives

The primary objective is to assess the effectiveness of a social incentive-based gamification intervention after radical cystectomy to increase physical activity postoperatively. We will explore patients' physical activity postoperatively at the time of discharge and if receiving the social intervention affects the amount of physical activity. A secondary objective will explore the effect of postoperative social incentives on improving physical activity at 3 months post-discharge. We will also explore changes in patient functional decline, cognitive function, postoperative delirium, SNF placement, readmission rates, and postoperative complication rates graded by the Clavien-Dindo classification.

## 3. Aims

### *3.1 Primary outcome*

The primary outcome variable is the change in mean daily step count from the baseline period after a radical cystectomy to the time of hospital discharge postoperatively.

### *3.2 Secondary outcome*

The secondary outcome variable is the change in mean daily step count from the postoperative baseline to 3 months after discharge from the hospital.

### *3.3 Exploratory outcome*

The exploratory outcome variable is a composite of placement to skilled nursing facility, 30-day hospital readmission, postoperative complication rates, cognitive function, postoperative delirium rates, and functional decline postoperatively.

## 4. Background

Treatment for bladder cancer is complex and disproportionately affects a vulnerable elderly population. The median age at diagnosis for bladder cancer is 73 years, and 30-60% of patients experiencing a postoperative complication with up to 30% readmitted within 90 days. Preliminary evidence suggests that mobility is a potential lever to improve postoperative complications and readmissions. However, only 1 in 4 hospitalized patients ever walk outside their room during hospitalization, and previously ambulatory patients spend 95% of their hospitalized time in bed. Despite a growing body of literature supporting the use of wearable technology to measure postoperative mobility, few studies evaluate how best to implement mobility interventions for elderly patients undergoing surgery. There is no data to show how much immobility is dangerous, and how much mobility is needed to prevent adverse outcomes after major surgery.

## **Study design**

### *5.1 Design*

We will conduct a two-arm randomized, controlled trial during the postoperative period after a radical cystectomy for bladder cancer, comparing a control group that uses a wearable device to track physical activity to an intervention group that uses the same wearable devices and receives a supportive social incentive-based gamification intervention to adhere to a step goal program. Patients will be enrolled after being diagnosed with bladder cancer and scheduled to undergo a radical cystectomy. The median length of stay after a radical cystectomy is 8 days, with 90% being discharged within two weeks. Postoperatively, the baseline step count will be averaged by taking the steps taken during the first two days outside of the intensive care unit. There will be two postoperative phases: Phase I will be while the patient is hospitalized postoperatively. Phase II will be when the patient is discharged for three months.

### *5.2 Study duration*

The study will begin in Summer 2019. The primary intervention period is from the time of diagnosis through the cystectomy and postoperative recovery to 3-months post-hospital discharge. We expect the entire study to take approximately 18 months to conduct and analyze outcomes.

### *5.3 Target population*

Adults age 18 years or older who have bladder cancer and are undergoing a radical cystectomy

### *5.4 Accrual*

We will aim to enroll and randomize 30 patients. We estimate that a sample size of at least 30 participants (15 per arm) will provide 80% power to detect a difference of 500 steps in the change in mean daily step count from baseline to discharge between intervention and control, using a 2-sided  $\alpha$  of 0.05, assuming a baseline mean preoperative step count of 4000 steps and mean postoperative step count of 1074 steps (SD 955 steps), and accounting for a 10% dropout rate.

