### *8.2 Procedures*

Each week, the research coordinator will use an electronic health record query to generate a list of patients that are diagnosed with bladder cancer and scheduled for a radical cystectomy. At enrollment, the research coordinator will administer two additional screening questions to determine eligibility (owns a smart phone and able to provide consent) via the RedCap portal. If the participant successfully passes the screening questions, the patient can be consented to the study. The research coordinator will next present a series of surveys to the patient to be completed through the Way to Health portal. These validated instruments include: the Pittsburgh Sleep Quality Index, Karolinska Scale, Activity of Daily Living-Instrumental Activities of Daily Living Survey, Life Space Activity Survey, Mini-Nutritional Assessment Survey, Edmonton Symptom Assessment Survey, Treatment Burden Questionnaire, Lubben's Social Network Scale, Self Rated Health Survey, and Dementia Tool.

After completing the enrollment assessment, the research coordinator will show patients how to use the wearable device which can be worn on wrist (like a watch), carried in any pocket, or clipped to hospital gown.

Upon enrollment after diagnosis of bladder cancer and scheduled for cystectomy, participants will use the watch for one week to ensure that the data is captured accurately. After the radical cystectomy, there will be a two-day run-in period to estimate postoperative baseline step counts for all patients. For all patients with a baseline step count, they will be randomly assigned to control or intervention using block sizes of two. After discharge, all participants will be notified to complete post-discharge baseline surveys.

Participants in the control group will continue to have data collected passively. Participants in the control arm will only receive study communications when it is time for them to complete surveys in the Way to Health system.

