Participants in the intervention arm will have a postoperative daily step goal that increases from baseline by 500 steps each day. At the beginning of each week, starting from the first day after the postoperative baseline is set (i.e. postoperative day 3), the participant receives 70 points (10 points for each day that week). If the participant does not meet their daily step goal, they lose 10 points from their balance. This leverages loss aversion, which has been demonstrated to motivate behavior change more effectively with losses than gains. At the end of each week if the participant has at least 40 points, they will move up a level (levels from lowest to highest: blue, bronze, silver, gold, platinum). If not, the participant will drop a level. All participants begin at the silver level. Each week, participants get a fresh set of 70 points. Participants will receive daily feedback for the step counts, and weekly feedback for their levels. Participants in the intervention arm will be asked to identify a family member or friend to be their support sponsor. A weekly report will be sent to this person with the participant's performance (points and level).

After discharge, the goals will be changed from daily step goals to weekly step goals to increase the weekly step counts by 10% each week to a maximum of 10,000 steps.

Participants in both arms will also receive a notification when it is time to complete surveys in the Way to Health system (5, 9, and 13 weeks after hospital discharge). 3 days after the surveys are sent to participants, a message will be sent reminding them to complete the surveys if they have not already done so. Upon completion of the final set of surveys, \$50 will be processed for participants in both arms.

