## **9. Analysis plan**

In our primary analyses, we will use multiple imputation for missing data and use linear mixed effects models to compare the change in mean daily step count from baseline to hospital discharge (ie postoperative Phase I time period), adjusting for baseline step count and time. To test of the robustness of our findings we will also evaluate models using collected data without imputation. All hypothesis tests will be two-sided using a two-sided alpha of 0.05 as our threshold for statistical significance. In secondary analyses, a similar linear mixed effects model

will compare the change in mean daily step counts from postoperative baseline to 3 months post-discharge (Phase II time period).

In exploratory analyses, we will evaluate how differences in postoperative step counts are associated with outcome measures. We will also conduct a qualitative analysis to evaluate participant perceptions of the intervention.

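### The 80% power stated in section 5.4 does not follow from its inputs: with 955 as the SD of the analysed quantity, power for 500 steps is about 26% to 28%, and no SD for the analysed change is given.

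*Combined protocol and SAP*

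**What the plan says.** Section 5.4 (Accrual) states that "30 participants (15 per arm) will provide 80% power to detect a difference of 500 steps" between arms in the change from baseline to discharge, at a two-sided alpha of 0.05 and allowing for 10% dropout. The calculation is described as "assuming a baseline mean preoperative step count of 4000 steps and mean postoperative step count of 1074 steps (SD 955 steps". No other SD appears in the document.

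The endpoint is described elsewhere. Section 3.1 defines it as "the change in mean daily step count from the baseline period after a radical cystectomy" to hospital discharge. Section 5.1 says that "the baseline step count will be averaged by taking the steps taken during the first two days outside of the intensive care unit", so the baseline is postoperative. Section 9 says the primary analysis will "use linear mixed effects models to compare the change in mean daily step count from baseline to hospital discharge", with adjustment for baseline steps and time. Section 8.2 says of patients with a baseline count that "they will be randomly assigned to control or intervention using block sizes of two", which gives 1:1 allocation.

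**The concern.** A 500-step difference against an SD of 955 is a standardised difference of 500/955 = 0.52. Fifteen patients per arm is far too few for 80% power at that size in a two-arm comparison of means. Either the analysed quantity has a much smaller SD than 955, in which case 5.4 leaves out the figure that carries the calculation, or the 80% is wrong.

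Section 5.4 also describes its baseline as a preoperative mean of 4000 steps, whereas the endpoint starts from a two-day postoperative baseline. That mean does not enter a between-arm power formula and does not change the arithmetic. It does mean that the calculation, as described, does not match the endpoint in 3.1 and 5.1.

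This paragraph is the only justification for the sample size of a trial with a formal primary test. Readers will take it that a 500-step effect would probably be detected. If power is much lower, a non-significant result says little about such an effect but may be reported as if it did.

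**Working it through.** **Inputs.** Section 5.4: difference 500 steps, SD 955, 15 per arm, two-sided alpha 0.05, dropout 10%. Assumption: dropout leaves 30 × 0.9 = 27 evaluable, or 13.5 per arm on average.

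**1. Attempt to reproduce the 80%, with 955 as the SD of the analysed quantity.** Two-sample t-test, noncentral t with SE = SD × √(2/n), noncentrality = 500/SE and df = 2n − 2.

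| | 15 per arm | 13.5 per arm |
|---|---|---|
| SE | 955 × √(2/15) = 348.7 | 955 × √(2/13.5) = 367.6 |
| Noncentrality | 1.434 | 1.360 |
| Power | 28.3% | 25.8% |
| Difference detectable with 80% power | 1,012 steps | 1,072 steps |
| Expected 95% CI half-width | 2.048 × 348.7 = 714 | 2.060 × 367.6 = 757 |
| SD that would give 80% at 500 steps | 472 | 446 |

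The normal approximation gives 29.9% and 27.4%. A one-sided test at 15 per arm gives 40.3%. For 80% power at 500 steps, 58 evaluable per arm gives 79.8% and 59 gives 80.5%. With 10% dropout that is 118/0.9 = 131.1, so 132 randomised.

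A one-sample test on all 30 patients, with no dropout, gives 79% (74.5% with 27). That may be where the 80% came from, but this is inference: the document names no formula, and a one-sample test is not the between-arm comparison described.

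**2. 955 as the SD of patient means at each time point, 27 evaluable.** Residual SD after baseline adjustment = 955 × √(1 − ρ²), with ρ the baseline/follow-up correlation (df 24).

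- ρ = 0.5: SD 827, power 33%.
- ρ = 0.7: SD 682, power 45%.
- 80% requires ρ of about 0.885.

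For an unadjusted change score, SD = 955 × √(2(1 − ρ)). Power is 15% at ρ = 0 and 26% at ρ = 0.5, and 80% requires ρ of about 0.891.

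**3. 955 as a single-day SD, with days averaged.** This is the reading most favourable to the plan. Its assumptions are mine: compound symmetry with between-day correlation ρ, two baseline days, k follow-up days averaged, the same k for everyone, and 27 evaluable (df 24). Residual variance = 955² × [(1 + (k − 1)ρ)/k − ρ²/((1 + ρ)/2)].

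Section 5.1 says "The median length of stay after a radical cystectomy is 8 days", and section 8.2 has the goals "starting from the first day after the postoperative baseline is set (i.e. postoperative day 3". Days 3 to 8 give k = 6 at the median stay.

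| ρ (k = 6) | 0 | 0.1 | 0.3 | 0.5 | 0.6 |
|---|---|---|---|---|---|
| Baseline-adjusted power | 89% | 77% | 70% | 74% | 80% |

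With six days, power is below 80% for ρ between about 0.07 and 0.60. The lowest power over ρ depends on the number of days:

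| k | 3 | 4 | 6 | 8 | 12 |
|---|---|---|---|---|---|
| Minimum power | 54% | 61% | 70% | 74% | 79% |

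With all 30 evaluable, the minimum at six days is 75%, and 80% holds at every ρ only with about ten or more days (82% at ten). An unadjusted change score with six days and 27 evaluable gives 36% at ρ = 0, 62% at ρ = 0.5, and 80% only at ρ of about 0.67.

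**The case against.** The strongest reply is that this shows a missing input, not a false 80%. Section 5.4 attaches 955 to the postoperative step count, not to the change, and section 9 adjusts for baseline in a mixed model on repeated counts. If the residual SD were about 446 to 472, 80% would be correct. That stands, and it is why the 26% to 28% is conditional on how 955 is read. It does not rescue 5.4, because neither that SD nor anything from which it could be derived is stated.

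A second objection is that the day-averaging calculation rests on assumptions found nowhere in the document. Six days is only the figure at the median stay; about half of patients would be expected to leave by then, and time in intensive care would delay the baseline and shorten follow-up. Nor does section 3.1 settle whether all inpatient days are averaged. This also stands: those figures show a range and should not be read as estimates. They do show that even a favourable reading does not secure 80% without a stated correlation and number of days.

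It is also fair to say that the 4000-step mean is a separate wording mismatch, that the pilot label is a choice of presentation, and that the remedy changes only text. None of this alters the main point.

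**Conclusion.** The concern holds. The 80% cannot be reproduced from the inputs in 5.4. Taken at face value, with 955 as the SD of the analysed quantity and 27 evaluable, power for 500 steps is about 26%, and the expected CI half-width of 757 steps exceeds the target difference.

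Whether true power is that low is unknown. If 955 is the SD of patient means, 80% needs a baseline/follow-up correlation of about 0.88 to 0.89, and an unadjusted change score could fall below 26%. If 955 is a single-day SD and six days are averaged under compound symmetry, baseline-adjusted power is at least about 70%, with less for shorter stays or no adjustment. The document does not say which case applies. Confidence is high that the stated power does not follow from the stated inputs; no single power figure can be put in its place without the missing ones. As the sole basis for the sample size, this must be corrected.

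**What to change.** Keep 30 patients and restate section 5.4.

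- **Preferred:** give the SD of the baseline-adjusted endpoint with its source, the baseline/follow-up correlation, the number of follow-up days averaged and the number evaluable. Say whether 955 is a single-day SD or an SD of patient means, and recompute power on that basis.
- **If 955 is the only SD available:** describe the trial as a pilot and state, as conditional on SD 955 and 27 evaluable, about 26% power for 500 steps, 80% power for about 1,070 steps, and an expected 95% CI half-width of about 757 steps.
- **In both cases:** align the baseline described in 5.4 with the two-day postoperative baseline in 3.1 and 5.1. Add one sentence to section 9 saying that the primary result is reported as an estimate with its 95% CI and that non-significance is not read as absence of effect.

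The cost is the wording of 5.4 and one sentence in section 9, with no extra patients and no change to procedures. The stated power will probably become less favourable.

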### *5.5 Key inclusion criteria*

1) Age 18 years or older; 2) diagnosis of bladder cancer undergoing a radical cystectomy

### *5.6 Key exclusion criteria*

1) Inability to provide informed consent; 2) does not have daily access to a smartphone compatible with the wearable device and not willing to use a device that we can provide them; 3) any other medical conditions that would prohibit participation in a physical activity program

## **6. Subject recruitment**

### *6.1 General*

The study team will use the electronic health record to identify potentially eligible patients in the Urology Department.

### *6.2 Populations vulnerable to undue influence or coercion*

Not applicable

## **7. Subject compensation**

Participants will receive \$25 for enrolling and \$25 for completing the discharge period, and \$50 for completing the 3-month post-discharge period. Compensation will be provided in a form of Greenphire ClinCard.

## **8. Study procedures**

### *8.1 Consent*

Potential subjects will first have the study fully explained to them and all questions will be answered, whereupon a written informed consent will be obtained. All aspects of the protocol and all procedures will be disclosed to the subject during this informed consent. Each subject will be told that he/she is free to discontinue participation in the study at any time and that the investigators also reserve the right to discontinue the study for medical or other reasons.

Participants will be provided with the paper consent form for signature and will be asked to either provide consent or decline participation in the study. In the paper copy of the consent, details regarding how to contact the research team via email or phone will be provided in the event a participant wants to withdraw from the study.

All patients who consent to this study will be debriefed in the same encounter during which they were approached.

- Clinical research coordinator will describe the study's use of deception and purpose.
- Patients will also be informed of reimbursement (total \$100)

### *8.2 Procedures*

Each week, the research coordinator will use an electronic health record query to generate a list of patients that are diagnosed with bladder cancer and scheduled for a radical cystectomy. At enrollment, the research coordinator will administer two additional screening questions to determine eligibility (owns a smart phone and able to provide consent) via the RedCap portal. If the participant successfully passes the screening questions, the patient can be consented to the study. The research coordinator will next present a series of surveys to the patient to be completed through the Way to Health portal. These validated instruments include: the Pittsburgh Sleep Quality Index, Karolinska Scale, Activity of Daily Living-Instrumental Activities of Daily Living Survey, Life Space Activity Survey, Mini-Nutritional Assessment Survey, Edmonton Symptom Assessment Survey, Treatment Burden Questionnaire, Lubben's Social Network Scale, Self Rated Health Survey, and Dementia Tool.

After completing the enrollment assessment, the research coordinator will show patients how to use the wearable device which can be worn on wrist (like a watch), carried in any pocket, or clipped to hospital gown.

Upon enrollment after diagnosis of bladder cancer and scheduled for cystectomy, participants will use the watch for one week to ensure that the data is captured accurately. After the radical cystectomy, there will be a two-day run-in period to estimate postoperative baseline step counts for all patients. For all patients with a baseline step count, they will be randomly assigned to control or intervention using block sizes of two. After discharge, all participants will be notified to complete post-discharge baseline surveys.

Participants in the control group will continue to have data collected passively. Participants in the control arm will only receive study communications when it is time for them to complete surveys in the Way to Health system.

Participants in the intervention arm will have a postoperative daily step goal that increases from baseline by 500 steps each day. At the beginning of each week, starting from the first day after the postoperative baseline is set (i.e. postoperative day 3), the participant receives 70 points (10 points for each day that week). If the participant does not meet their daily step goal, they lose 10 points from their balance. This leverages loss aversion, which has been demonstrated to motivate behavior change more effectively with losses than gains. At the end of each week if the participant has at least 40 points, they will move up a level (levels from lowest to highest: blue, bronze, silver, gold, platinum). If not, the participant will drop a level. All participants begin at the silver level. Each week, participants get a fresh set of 70 points. Participants will receive daily feedback for the step counts, and weekly feedback for their levels. Participants in the intervention arm will be asked to identify a family member or friend to be their support sponsor. A weekly report will be sent to this person with the participant's performance (points and level).

After discharge, the goals will be changed from daily step goals to weekly step goals to increase the weekly step counts by 10% each week to a maximum of 10,000 steps.

Participants in both arms will also receive a notification when it is time to complete surveys in the Way to Health system (5, 9, and 13 weeks after hospital discharge). 3 days after the surveys are sent to participants, a message will be sent reminding them to complete the surveys if they have not already done so. Upon completion of the final set of surveys, \$50 will be processed for participants in both arms.

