### *11.5 Safety monitoring*

At the time of enrollment in the hospital, all patients will be given anticipatory guidance on when to seek medical attention (e.g. when to call their nurse or doctor should they feel dizzy, short of breath, chest pain, lightheaded, unstable, or otherwise unwell while ambulating). In addition, participants will be asked to report to the study team any episodes of these symptoms that occur during ambulation during visits with research staff (the research assistant will check in periodically with enrolled patients to ensure devices are working properly and troubleshoot any issues encountered by patients/caregivers or nursing). Patients/caregivers will also be reminded that they can always contact the study team by phone or email at any time (contact information will be given at the beginning of the study and will also be posted on the Way to Health platform, which can be accessed at any time by the participant). If any concerns of a participant event are identified, the study coordinator will reach out to the participant and complete the event reporting form. This form will be reviewed with the study PI to determine if any action is needed and if the participant can continue safely in the study. Any identified adverse events will be reported to the Institutional Review Board. For patients on floors where the mobility protocol is in place, mobility goals are revised daily by the bedside nurse caring for the patient. If patient is noted to be weaker, the nurse will automatically reduce the mobility goal for the day per the mobility protocol (this happens without regard to research protocol).

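### Fixed blocks of two make 15 of the 30 allocations certain to anyone who follows the sequence; varied, undisclosed blocks released after a baseline lock would be a cheap improvement

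*Combined protocol and SAP*

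**What the plan says.** Section 8.2 (Procedures) describes a two-day run-in after cystectomy to estimate the postoperative baseline. For patients who have a baseline count, "they will be randomly assigned to control or intervention using block sizes of two". No other block size and no stratification is given. Section 5.4 (Accrual) sets 30 patients, 15 per arm.

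The arms differ openly. Intervention patients receive step goals, points, levels and daily feedback, and "Participants in the intervention arm will be asked to identify a family member or friend to be their support sponsor". By contrast, "Participants in the control arm will only receive study communications when it is time for them to complete surveys". Under section 11.5 (Safety monitoring), "the research assistant will check in periodically with enrolled patients to ensure devices are working properly and troubleshoot any issues".

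On the baseline, section 5.1 (Design) says "the baseline step count will be averaged by taking the steps taken during the first two days outside of the intensive care unit". Before surgery, "participants will use the watch for one week to ensure that the data is captured accurately". No section available to this review says who holds the list, how assignments are concealed, or what makes a baseline count usable.

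**The concern.** Two is the smallest possible block for two arms, so this is the most predictable blocked scheme available, and the protocol prints the size. Anyone who knows the position within each pair knows every second assignment before it is made.

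The measurement exposed to that foreknowledge is the postoperative baseline, because it is collected just before assignment and is used four times:

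- it is the condition for being randomised (8.2);
- it is the starting point for the intervention arm's goals (8.2);
- it is the reference for the change that forms the primary outcome (3.1);
- it is a covariate in the primary mixed model (section 9).

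Two openings remain. One is the decision whether a patient has a usable baseline. The other is how much walking is encouraged during the run-in. If either depended on the expected arm, the primary comparison would be affected directly.

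**Working it through.** **Inputs.** Two arms (5.1); 30 patients, 15 per arm (5.4); fixed blocks of two (8.2). Assumption: one unstratified list. The only figure of the plan used here is the 30. The power claim behind it is a separate matter; its printed inputs appear only in step 4.

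**1. Blocks of two**

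- Pairs: 30 / 2 = 15. The second assignment of each pair is fixed, so 15 of 30 (50%) are certain.
- Best guess by someone who follows the sequence: (15 × 1 + 15 × 0.5) / 30 = 22.5 / 30 = 75%.
- Someone who knows only the last assignment, not its position, and guesses the opposite arm: of 29 transitions, 15 fall within a pair (always opposite) and 14 between pairs (opposite half the time). (15 × 1 + 14 × 0.5) / 29 = 22 / 29 = 76%.

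**2. Randomly varied blocks of 4 and 6, equally likely (sizes assumed for illustration)**

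- Sizes undisclosed: the guesser knows only that each block is 4 or 6 and updates by Bayes' rule after each assignment. Simulating 15,000 lists gives 1.73 of 30 certain (5.8%) and 68.8% of best guesses correct.
- Only the last assignment known: neighbours within a block of size b are opposite with probability (b/2)/(b − 1), which is 2/3 for 4 and 3/5 for 6; across a block boundary it is 1/2. Exact recursion over the 29 transitions gives 60.3%.
- If each block's size became known, exact recursion gives 8.10 of 30 certain (27.0%).

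| | Blocks of 2 | Undisclosed 4 and 6 |
|---|---|---|
| Certain allocations, of 30 | 15 (50%) | about 1.7 (6%) |
| Best guesses correct, sequence followed | 75% | about 69% |
| Opposite of last assignment correct | 76% | 60% |

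**3. Balance given up**

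Blocks of two keep the arms within one patient wherever accrual stops. With blocks of 4 and 6 (exact recursion):

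- at 30 patients: equal arms in 77.3% of lists, 14 v 16 in 22.7%;
- stopping at an even total from 16 to 28: a difference of two in 21.3% to 23.5%;
- stopping at an odd total from 15 to 29: a difference of three in 1.9% to 2.2%, and never more than three.

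**4. Power cost of imbalance**

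Two-sample t test, two-sided alpha 0.05, at a standardised effect of 1.06, chosen because it gives 80% with 15 v 15:

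| Total | Near-equal split | Less equal split |
|---|---|---|
| 30 | 15 v 15: 80.0% | 14 v 16: 79.8% |
| 27 | 13 v 14: 75.3% | 12 v 15: 74.9% |
| 21 | 10 v 11: 63.4% | 9 v 12: 62.6% |

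These percentages are illustrative. With the effect and SD printed in 5.4 (500/955 = 0.52), power is 28.3% for 15 v 15 and 28.2% for 14 v 16, so the cost of imbalance is small either way.

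**The case against.** The strongest reply is that the route to harm is narrow, and much of that stands. Consent precedes surgery, so foreknowledge cannot easily steer who is enrolled. Steps come from a device tried before surgery, and points start only after the baseline is set. That staff know earlier assignments is an inference; no available section says so. Section 11.5 gives the research assistant's check-ins a device-support purpose. It also has bedside nurses adjusting mobility goals independently of the research on floors with a mobility protocol. Section 11.6.4 gives every patient usual physical therapy and nursing help. These points weaken the run-in route without closing it, because the mobility protocol covers only some floors.

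Second, the gain in average guessing is modest: 75% to about 69%. That is correct. The larger gain is in certainty, which falls from 15 allocations to about 1.7, and certainty is what would allow deliberate action.

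Third, a baseline lock and a usable-baseline rule would help under any block size. That is also true. They act on the remaining route and complement the block change.

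Nor is the baseline window wholly settled. Section 5.1 counts from leaving intensive care, while 8.2 equates the first day after baseline with postoperative day 3. The two can disagree for a patient with an intensive care stay and need to be reconciled. This leaves more room for discretion, not less.

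**Conclusion.** The concern holds as a design improvement that should be made; it does not invalidate the trial. Under the stated scheme, half the allocations are certain to anyone who follows the sequence. This rests on the text of 5.4 and 8.2 and on there being a single unstratified list. Confidence is medium, because custody of the list and staff knowledge of past assignments are not stated. No bias in step counts is claimed: the documents give no figure for how far walking or baseline acceptance could be influenced during the run-in.

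**What to change.** In section 8.2, replace the block-size phrase with wording such as:

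> from a computer-generated list in randomly varied, undisclosed blocks, not visible to staff who enrol or check in with patients. Each assignment is released only after that patient's baseline step count has been locked under a usable-baseline rule that is fixed in advance and applied without regard to the expected assignment.

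Record the block sizes (for example 4 and 6) in a restricted file, not in the protocol; if they became known, about 8 of 30 allocations would again be certain.

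**Cost.** Two sentences, a short usable-baseline rule and a new list, with no extra patients or staff. The trial gives up guaranteed near-equal arms, at the small power cost shown above.

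**Limits.** The lock prevents changes to the baseline after release, and the rule settles which baselines count. Neither removes all influence on walking during the run-in.
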